7.1.5. Lead-In Period

Eligible subjects will begin a 2-week lead-in period at Visit 2 (Week -2) according to the Study Schedule ([Attachment 1](#)). The lead-in period is intended to stabilize HbA1c related to study effect (Gale et al. 2007) and verify insulin dose. Subjects entering the trial at Visit 1 will continue their pre-study insulin regimen. Subjects will also continue taking pre-study AHA regimens and doses (per inclusion/exclusion criteria in Sections 8.1 and 8.2) and should not discontinue or change doses during the study, apart from specific instructions provided in Section 9.11.

7.1.6. Randomization

Study subjects who have completed all screening procedures will be randomized at a 1:1 ratio to the two treatment arms (U-500R CSII or MDI) using interactive web-response system (IWRS) at Visit 4 (Section 9.6).

A review of subjects' understanding of daily glucose monitoring and emphasis on adherence, 4-point and 7-point SMBG profile, use of glucose meters, hypo- and hyperglycemia, and completion of subjects' diary will be conducted.

7.1.7. Treatment Period

At Visit 4 through Visit 17 or ET, subjects will be treated with U-500R based on titration algorithms. The total treatment period for this study will be 26 weeks (2 week transition to U-500R MDI administered TID, 12 weeks titration and 12 weeks maintenance U-500R CSII or MDI).

During the Treatment Period, Visits 8, 9, 11, 12, 14, and 16 will be telephone visits only and subjects will not be required to return to the study site. At office visits (Visits 5, 6, 7, 10, 13, 15,

and 17), clinical assessments and required procedures should occur as outlined in the Study Schedule ([Attachment 1](#)). Adverse event and product complaint collection should occur at each office and telephone visit.

Apart from scheduled telephone visits, per the Study Schedule ([Attachment 1](#)), subjects will be instructed to call the study site office if a serious adverse event (SAE) or device-related event occurs, or for any concern at any time. Specific reasons may include but are not limited to: hospital admission for any reason, persistent or severe hypoglycemia, recommendations for changes of medication from another provider, injection device or study glucose meter malfunction, questions about study treatment and dose changes, or scheduled surgical or dental procedures.

Subjects will continue taking noninsulin pre-study AHAs (per inclusion/exclusion criteria in Sections [8.1](#) and [8.2](#) and allowed concomitant therapies in Section [9.11](#)) and should not discontinue or change doses during the study.

7.1.7.1. Transition to U-500R MDI

A 2-week transition period is included in the 26-week treatment period and will follow randomization. The transition period is intended to transition all subjects safely from their current insulin regimen to U-500R TID 40:30:30 (Section [9.5](#)), and to titrate U-500R according to the TID algorithm (Section [9.8.2.1](#)). The highest 24-hour TDD from the past 3 days will be utilized for calculation of the U-500R TID dose and the dose split into the ratio of 40:30:30. Those subjects already on U-500R TID at entry can continue their pre-entry U-500R TID proportions at the discretion of the investigator. At Visit 6 through Visit 17 or ET, subjects will be treated with either U-500R CSII (Section [9.8.1.1](#)) or U-500R MDI delivered TID (Section [9.8.2.1](#)) based on titration algorithms and the treatment to which they are randomized.

7.1.7.2. U-100 Insulin Syringe for Administering U-500R MDI

All subjects will receive training on the appropriate use of U-100 insulin syringes for drawing up and administering correct doses of U-500R, including the conversion of insulin units of U-500R to the unit markings (one-fifth of actual volume) on the U-100 insulin syringe (Section [9.7.1](#)).

7.1.7.3. CSII Pump Training

Subjects assigned to U-500R CSII treatment will receive training on the OmniPod U-500 system at 2 visits (Visit 5 [Week 1] and Visit 6 (Week 2)). At Visit 5, subjects will be introduced to the basics of pump usage (ie, basal rates, boluses, and filling Pods). At Visit 6, subjects will receive hands-on training on the U-500 OmniPod System. Additional subject training can be considered at the investigator's discretion after consulting with Lilly clinical research physician (CRP)/clinical research scientist (CRS) (Section [9.7.2](#)).

7.2. Discussion of Design and Control

This is a randomized, open-label, parallel study comparing U-500R administered by CSII (OmniPod U-500 system) to U-500R administered by MDI in high-dose insulin-requiring patients with T2DM who have inadequate glycemic control on existing high-dose non U-500R (>200 and ≤600 units per day) insulins (CSII or MDI), and/or U-500R insulin MDI with or

without other insulins/AHAs. Delivery of U-500R insulin by CSII in currently marketed insulin pumps requires dose conversion to “U-100 pump units” (one-fifth of U-500R insulin dose per volume), which potentially could result in dosing confusion. The OmniPod Insulin Management System for use with U-500 insulin (OmniPod U-500 system) software has been developed so that 1 unit of insulin is delivered with every 4 pulses of the drive mechanism (for example, the OmniPod U-500 system would deliver 0.25 units per pulse compared to 0.05 units per pulse in the conventional U-100 OmniPod insulin pump). The volume delivered in 1 pulse is the same for the U-100 and U-500 insulin pumps; thus due to higher concentration, fewer pulses are required by the U-500 pump to deliver the same insulin dose (4 pulses for 1-unit for U-500 insulin versus 20 pulses for 1-unit for U-100 insulin).

The majority (86%) of patients currently using U-500R have T2DM (Eby et al. 2013). Because patients with type 1 diabetes mellitus (T1DM) constitute a small proportion of U-500R users and could have a different response to the algorithms and/or CSII delivery system, they are excluded from this study.

The total treatment period for this study will be 26 weeks. The 26-week duration of treatment in this study was selected because it allows enough time for insulin therapy to be intensified, and permits sufficient time to show glycemic improvement and stabilization as measured by HbA1c, FPG, SMBG values, and TDD.

After Visit 1 (screening), subjects who meet all of the inclusion criteria (Section 8.1) and none of the exclusion criteria (Section 8.2) will remain on their pre-study treatment for a 2 week lead-in period at Visit 2 (Week -2). This lead-in period is intended to stabilize HbA1c related to study effect (Gale et al. 2007) and verify actual insulin dose. Following the lead-in, subjects will be randomized at Visit 4 (Week 0) in an open-label fashion based on a 1:1 ratio to U-500R treatment by MDI or U-500R treatment by CSII. A 2-week transition to U-500R by MDI administered T1D, regardless of insulin or combination thereof at Visit 2 (Week -2) (Section 9.5) will begin after randomization (Visit 4 [Week 0]) utilizing the T1D algorithm with weekly titrations (Section 9.8.2.1). The transition period is to ensure safe transition to U-500R insulin monotherapy from entry insulin (as applicable). After completion of the 2-week transition period, 24-weeks of U-500R delivered by MDI versus CSII will begin.

The primary and key secondary objectives will be assessed in subjects from Group A (without use of GLP-1 receptor agonists or SGLT2 inhibitors) and combined for the total study population Group A and Group B (those who use GLP-1 receptor agonists or SGLT2 inhibitors).

The study will be performed open-label since blinding of the investigators, subjects, and study site personnel could not be accomplished given the differing modes of delivery of U-500R (CSII versus MDI). To minimize bias, aggregate review of summary data by the study team (that is, CRP/CRS overseeing the global conduct of the study, statisticians, and statistical analysts) will remain blinded until after the final database is locked (Section 9.10).

8. Study Population

Individuals who do not meet the inclusion criteria for participation in this study (screen failure) may be re-screened once. The interval between screen and re-screen should be at least 2 weeks. When re-screening is performed, the individual must sign a new informed consent form (ICF) and will be assigned a new identification number.

Entered subjects who meet all inclusion criteria ([1] through [7]) and are not excluded by exclusion criteria ([8] through [28]) will initiate the lead-in period at Visit 2 (Week -2).

Prior to randomization at Visit 4, all subjects will be re-confirmed for inclusion criteria [1], [2] and [7] and exclusion criteria [18].

Prospective approval of protocol deviations to recruitment and enrollment criteria, also known as protocol waivers or exemptions, is not permitted.

8.1. Inclusion Criteria

Subjects are eligible to be included in the study only if they meet all of the following criteria:

- [1] Diagnosed with T2DM (World Health Organization [WHO] Classification of Diabetes [[Attachment 3](#)]).
- [2] For 2 weeks prior to Visit 1, TDD >200 but \leq 600 units of non U-500R insulin/analog (basal; premixed; or basal/bolus by any injection device [MDI; pens and/or syringe/vial or CSII]) and/or U-500R by MDI with syringe and vial. Type of insulin must be stable for \geq 3 months at entry.
 - If TDD of U-500R and other insulins are combined, then insulin other than U-500R not to exceed 25% of TDD.
- [3] HbA1c \geq 7.5% and \leq 12.0% as measured by the central laboratory at Visit 1.
- [4] Aged \geq 18 to \leq 85 years.
- [5] Body mass index \geq 25 but \leq 50 kg/m².
- [6] Have a history of stable body weight (not varying by greater than 5% for at least 3 months prior to study entry).
- [7] Concomitant AHA therapy may include metformin (MET), dipeptidyl peptidase-4 inhibitors (sitagliptin, saxagliptin, linagliptin, and alogliptin), and/or pioglitazone (doses \leq 30 mg/day). Subjects' AHA therapy must have been stable for \geq 3 months. See exclusion criteria [18] and [19] for excluded medications.

- Approximately 64 to 96 subjects using GLP-1 receptor agonists (albiglutide, dulaglutide, or liraglutide) or SGLT2 inhibitors (canagliflozin, dapagliflozin, empagliflozin) will be enrolled in Study Group B. (GLP-1 receptor agonists must have been stable for ≥ 4 months). After the enrollment of this group is completed, subjects using GLP-1 receptor agonists or SGLT2 inhibitors will no longer be enrolled in the study. After Group A has been fully enrolled, Lilly may stop enrollment for Group B, even if the minimum recruitment goal for Group B has not been met.

8.2. Exclusion Criteria

Subjects will be excluded from study if they meet any of the following criteria:

- [8] Diagnosed with T1DM or other types of diabetes apart from T2DM (WHO Classification of Diabetes [Attachment 3](#); ADA 2014).
- [9] Have obvious clinical or radiographic signs or symptoms of liver disease (except nonalcoholic fatty liver disease), cirrhosis, acute or chronic hepatitis, or alanine aminotransferase (ALT/SGPT) and/or aspartate aminotransferase (AST/SGOT) levels $\geq 2.5X$ upper limit of normal (ULN), alkaline phosphatase $\geq 2X$ ULN or total bilirubin $\geq 2X$ ULN (with the exception of known Gilbert syndrome) as defined by central laboratory.
- [10] Have chronic kidney disease Stage 4 and higher (estimated glomerular filtration rate < 30 mL/minute/1.73m² as measured by Modification of Diet in Renal Disease [MDRD] formula) (NKF 2007) or history of renal transplantation.
- [11] Have history of more than 1 episode of severe hypoglycemia requiring assistance of another person, resulting in coma, seizures, or disorientation within the 6 months prior to Visit 1.
- [12] Have received U-500R insulin by CSII in the 3 months prior to Visit 1.
- [13] Have had a blood transfusion or severe blood loss within 3 months prior to Visit 1 or have known hemoglobinopathy, hemolytic anemia, or sickle cell anemia that is known to interfere with HbA1c measurement.
- [14] Have known allergy to human insulin preparations or excipients contained in these products or prior history of suspected antibodies to human insulin.
- [15] Are taking chronic (lasting longer than 14 consecutive days) systemic glucocorticoid therapy (excluding topical, intra-articular, intraocular, and inhaled prescriptions), or have received any systemic glucocorticoid therapy within the 4 weeks immediately prior to Visit 1.
- [16] Have an irregular sleep/wake cycle (for example, subjects who sleep during the day and work during the night), in the investigator's opinion.
- [17] Intend to participate in an extended period of fasting during the study period (for religious or other purposes).

- [18] Have used rosiglitazone, sulfonylurea/glinides, pramlintide, once-weekly or twice-daily exenatide, or other AHAs not listed in the inclusion criteria in the 3 months prior to Visit 1, are taking AHA doses exceeding the respective product labels, or have a contraindication to current AHA usage per respective product labels (for example, for MET: serum creatinine ≥ 1.4 mg/dL in women or ≥ 1.5 mg/dL in men).
- [19] Have used any weight loss drugs (for example, prescription drugs; lorcaserin, orlistat, phentermine, phentermine/topiramate, naltrexone/bupropion, or over-the-counter weight loss medications or herbal supplements) in the 3 months prior to Visit 1.
- [20] Have a history of bariatric surgery including Roux-en-Y gastric bypass surgery, gastric banding, and/or gastric sleeve.
- [21] Have a history of an active or untreated malignancy, or in remission from a clinically significant malignancy (other than basal cell or squamous cell skin cancer, in situ carcinomas of the cervix, colon, or prostate that is considered cured) during the last 5 years before Visit 1 (if a malignancy occurred >5 years ago, subject is eligible with documentation of disease-free state since treatment).
- [22] Significant hearing loss and/or vision impairment deemed by the investigator to interfere with the safe use of OmniPod U-500 system.
- [23] Have cardiac disease with functional status that is New York Heart Association (NYHA) Class III or IV per New York Heart Association Cardiac Disease Functional Classification [[Attachment 4](#)].
- [24] Are women breastfeeding or pregnant, or intend to become pregnant during the course of the study; are men who intend to impregnate their partners; or are sexually active of procreation potential not actively practicing birth control by a method determined by the investigator to be medically acceptable.
- [25] Are investigator site personnel directly affiliated with this study and/or their immediate families. Immediate family is defined as a spouse, parent, child, or sibling, whether biological or legally adopted.
- [26] Are Lilly or Insulet employees, or are employees of third party organizations (TPOs) involved in study that require exclusion of their employees.
- [27] Are currently enrolled in, or discontinued within the last 30 days, from a clinical trial involving an investigational product or nonapproved use of a drug or device (other than the study treatment used in this study), or concurrently enrolled in any other type of medical research judged not to be scientifically or medically compatible with this study, and any subjects who have previously completed or withdrawn from this study.

- [28] Are unwilling or unable to independently perform study procedures, such as monitoring SMBG levels, recording diary data, and/or administering medication via syringe or CSII as applicable, or have any illness or condition (including known drug or alcohol abuse or psychiatric disorder) within the 6 months prior to Visit 1, that precludes subject from following and completing the protocol according to the investigator's judgment. Subjects may not use a proxy to perform collection procedures, administer medication, or record data.

8.2.1. Rationale for Exclusion of Certain Study Candidates

Exclusion criterion [8] ensures that subjects with T1DM or other types of diabetes (except T2DM) will be excluded from the study due to the potentially different response to the algorithms and/or device. Exclusion criteria [9], [10], [13], [14], [16], [17], [21], and [23] represent clinical situations that may prevent subjects from completing the protocol, or may influence the efficacy or safety of study regimens, or are serious conditions that pose a risk for morbidity and mortality. Exclusion criterion [11] addresses the potential difficulty of distinguishing if severe hypoglycemia is related to study drugs, or to counter-regulatory deficiencies, or to the natural history of the disease in subjects with recurring episodes. Exclusion criterion [12] relates to the potential of sub-optimal glycemic control and possible changes in quality of life when changing from U-500R CSII therapy. Exclusion criterion [15] relates to the negative effect of steroid therapy on the management of diabetes and need for altered dosing titration of insulin. Exclusion criterion [18] excludes medications that are restricted by product label (exenatide), may cause HbA1c-lowering not attributable to the study insulin regimens or the combination of AHAs being studied, or which could confound interpretation of the results, or may influence the safety of study regimens. Exclusion criteria [19], [20] and [27] prevent a situation in which positive or negative outcomes may not be clearly attributable to the regimens in this study. Exclusion criterion [22] would prevent the subject from safely using the OmniPod U-500 system. Exclusion criterion [24] ensures the safety of unborn or newborn children. Exclusion criteria [25] and [26] reduce potential bias due to conflict of interest. Exclusion criterion [28] excludes subjects who may be unwilling or unable to perform study procedures per protocol instructions for their safety.

8.3. Discontinuations

8.3.1. Discontinuation of Inadvertently Enrolled Subjects

The criteria for enrollment must be followed explicitly. If the investigator site identifies a subject who did not meet enrollment criteria and who was inadvertently enrolled, the sponsor must be notified. If the sponsor identifies a subject who did not meet enrollment criteria and who was inadvertently enrolled, the investigator site will be notified. A discussion must occur between the sponsor CRP/CRS and the investigator to determine whether the subject may continue in the study, with or without study treatment. Inadvertently enrolled subjects may be maintained in the study and on study treatment when the Lilly CRP/CRS agrees with the investigator that it is medically appropriate for that subject. The subject may not continue in the study with or without study treatment if the Lilly CRP/CRS does not agree with the

investigator's determination it is medically appropriate for the subject to continue. The investigator must obtain documented approval from the Lilly CRP/CRS to allow the inadvertently enrolled subject to continue in the study with or without study treatment.

8.3.2. Discontinuation of Study Treatment

Subjects will be discontinued from the study treatment in the following circumstances:

- If Exclusion Criteria [9] (with the exception of the hepatic laboratory values; Section 10.4.4), [11] to [15], [18] to [21], [23] and [24] are observed or develop after study enrollment, the subject will be discontinued from the study treatment at the next visit or sooner.
- If in the investigators judgment, the subject is not at least 80% compliant with study treatment (i.e.; investigator recommended dose adjustments based on algorithms)
- If the subject is off study medication for more than 7 consecutive days during the study treatment period.

In the event that the subject is discontinued from the study treatment, the investigator should encourage the subject to remain in the study for continued safety monitoring.

8.3.3. Subject Discontinuation from the Study

If exclusion criterion [25] through [28] is observed or develops after entry or enrollment, the subject will be discontinued from the study at the next site visit or sooner in the event of a safety exclusion criterion.

Subjects who discontinue the study early will have ET procedures performed as shown in the Study Schedule ([Attachment 1](#)). For information as to how efficacy and safety analyses will be conducted for subjects who are discontinued from study treatment, see Sections 12.2.3 and 12.2.10, respectively.

The subject may be discontinued from the study if:

- Enrollment in any other clinical trial involving an investigational product or enrollment in any other type of medical research judged not to be scientifically or medically compatible with this study.
- Investigator decision
 - The investigator decides that the subject should be discontinued from the study (this can be for safety reasons, such as for recurrent hypoglycemia, or it can be for any reason).
 - If the subject, for any reason, requires treatment with another therapeutic agent that has been demonstrated to be effective for treatment of the study indication, discontinuation from the study occurs prior to introduction of the new agent.
- Subject decision
 - The subject requests to be withdrawn from the study.

- Sponsor decision
 - Lilly or its designee stops the study or stops the subject's participation in the study for medical, safety, regulatory, or other reasons consistent with applicable laws, regulations, and good clinical practice (GCP).
- Adverse event
 - If the investigator decides that the subject should be withdrawn because of a SAE, treatment emergent adverse event (TEAE), or a clinically significant laboratory value, study treatment is to be discontinued and appropriate measures are to be taken. Lilly or its designee is to be alerted immediately. Refer to Safety Evaluations Section [10.4](#).

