9.12. Treatment Compliance

Subject compliance with study medication will be assessed at each applicable study visit.

Compliance will be based on adherence to the Study Schedule ([Attachment 1](#)), compliance with appropriate assigned injection method (CSII versus MDI), completion of the subject's diary, and any other parameters the investigator deems necessary. Compliance will be assessed by direct questioning and returned study materials.

Subjects who are deemed significantly noncompliant will be discontinued from the study treatment. A subject will be considered significantly noncompliant if he or she:

- misses more than 7 consecutive days of study medication during the study.
- is judged by the investigator to have intentionally or repeatedly taken more than the prescribed amount of medication that may cause patient safety concerns.
- is not at least 80% compliant with study treatment (ie, PI recommended doses adjustments based on algorithms).

10. Efficacy, Patient Reported Outcomes, Safety Evaluations, Sample Collection and Testing, and Appropriateness of Measurements

Study procedures and their timing (including tolerance limits for timing) are summarized in the Study Schedule ([Attachment 1](#)).

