10.6. Appropriateness of Measurements

All efficacy and safety assessments included in this study are generally regarded as reliable and accurate with respect to management of T2DM.

11. Data Quality Assurance

To ensure accurate, complete, and reliable data, Lilly or its representatives will do the following:

- Provide instructional material to the study sites, as appropriate.
- Provide start-up training to instruct the investigators and study coordinators. This training will give instruction on the protocol, the completion of the eCRFs, and study procedures.
- Make periodic visits to the study site.
- Be available for consultation and stay in contact with the study site personnel by mail, telephone, and/or fax.
- Review and evaluate eCRF data and use standard computer edits to detect errors in data collection.
- Conduct a quality review of the database.

To reduce missing data in the study, subjects who are discontinued from study treatment before study completion will be encouraged to remain in the study for continued safety monitoring (see Section 8.3.2). In addition, study site investigators will be trained on the importance of complete data collection.

Lilly or its representatives will periodically check a sample of the subject data recorded against source documents at the study site. The study may be audited by Lilly or its representatives, and/or regulatory agencies at any time. Investigators will be given notice before an audit occurs.

To ensure the safety of participants in the study, and to ensure accurate, complete, and reliable data, the investigator will keep records of laboratory tests, clinical notes, and subject medical records in the subject files as original source documents for the study. If requested, the investigator will provide the Sponsor, applicable regulatory agencies, and applicable ERBs with direct access to original source documents.

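### Protocol 8.3.3 ends follow-up when criterion [28] develops after enrollment, in conflict with 8.3.2, 9.12 and Section 11, and so costs the FDA-requested analysis Week 26 HbA1c values, plausibly more often in the CSII arm

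*Protocol*

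**What the plan says.** Protocol 8.3.3 is mandatory in tone: "If exclusion criterion [25] through [28] is observed or develops after entry or enrollment, the subject will be discontinued from the study". Criterion [28] in Protocol 8.2 covers subjects who will not or cannot carry out study tasks themselves. The tasks named are glucose monitoring, diary entries and "administering medication via syringe or CSII as applicable". It also covers illnesses or conditions that stop a subject from following the protocol.

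Protocol 8.3.2 lists the criteria that stop study treatment only: [9] in part, [11] to [15], [18] to [21], [23] and [24]. It adds compliance below 80% and more than 7 consecutive days off study medication. Criterion [28] is not on the list. For those who stop treatment, 8.3.2 says that "the investigator should encourage the subject to remain in the study for continued safety monitoring".

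Protocol 9.12 counts adherence to the assigned delivery method among the bases for judging compliance, and says: "Subjects who are deemed significantly noncompliant will be discontinued from the study treatment". Protocol Section 11, as a measure against missing data, says that "subjects who are discontinued from study treatment before study completion will be encouraged to remain in the study".

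The SAP's table of important deviations (Section 5.8) includes, as item 42, a subject who was not taken off treatment or off study when Protocol 8.3.2 or 8.3.3 required it. That item excludes the subject from the per-protocol population.

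**The concern.** The FDA-requested primary method (Protocol 12.2.7, SAP 5.9) is a treatment-policy analysis: it uses HbA1c measured after study treatment has stopped. It works only if people who stop treatment are still measured at Week 26. The 8.3.3 rule on [28] removes from follow-up some subjects whose post-treatment outcome the method is meant to capture. Amendment (a) rewrote the missing-data analyses, but Section 8.3 is not among the sections it revised.

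The losses may also differ by arm. All subjects inject U-500R by syringe in Weeks 0 to 2. Only the CSII arm then has to learn and keep using an investigational pump. A subject who gives up on the pump is a candidate for exit under [28], and the MDI arm has no direct counterpart. In an open-label noninferiority comparison, missing values that depend on arm and outcome can move the estimate toward a finding of noninferiority.

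**Working it through.** **1. The plan's own figure.** Inputs from Protocol 12.1 and SAP 5.1: margin 0.4, SD 1.1, two-sided alpha 0.05, 240 completers (120 per arm), 25% dropout. The true difference is not stated and is taken as 0.
- SE = 1.1 × √(2/120) = 0.142.
- Power = Φ(0.4/0.142 − 1.96) = 80.4%, against a stated 80%.
- Randomized = 240/0.75 = 320, as stated.

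**2. What a [28] withdrawal leaves behind.** "Subjects who discontinue the study early will have ET procedures performed", and Attachment 1 marks HbA1c at the early-termination visit. After Visit 4 the next scheduled HbA1c is Visit 10 (Week 8). CSII begins at Visit 6 (Week 2). A subject who refuses the pump at about Visit 6 therefore contributes a baseline value and an early-termination value near Week 2, which says little about Week 26.

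**3. Which analysis is affected.**
- *Copy-reference analysis.* It loses an observed Week 26 value and imputes one. In SAP 5.9 the donors are MDI subjects who stopped treatment and still completed the study. If they are too few, the donors are all MDI subjects with no missing data. A missing CSII value is thus filled from MDI experience.
- *MMRM.* It excludes data after treatment discontinuation, so retaining the subject changes little.
- *Stress test.* Deltas of 0.1 to 0.4 are added to imputed CSII values, but only as a sensitivity analysis of the MMRM. No delta analysis is specified for the copy-reference method.

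**4. Loss of power.** Suppose the [28] losses come on top of the planned 25% in the CSII arm, so that SE = 1.1 × √(1/n_CSII + 1/120).
- 5% extra (112 vs 120 completers): power 79.0%.
- 10% extra (104 vs 120): power 77.5%.

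**5. Shift in the estimate (illustration).** Let p be the share of the 160 Group A CSII subjects lost under [28]. Let g be how much worse their true Week 26 HbA1c is than the imputed value. The documents give neither; both ranges are assumed. The CSII-minus-MDI difference is understated by b = p × g. When the true difference equals the margin, the chance of wrongly declaring noninferiority is Φ(b/0.142 − 1.96), nominally 2.5%.

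| p (subjects) | g | b | b/0.4 | False noninferiority |
|---|---|---|---|---|
| 5% (8) | 0.5 | 0.025 | 6% | 3.7% |
| 5% (8) | 1.0 | 0.05 | 12.5% | 5.4% |
| 10% (16) | 0.5 | 0.05 | 12.5% | 5.4% |
| 10% (16) | 1.0 | 0.10 | 25% | 10.5% |

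For scale, 25% dropout is 40 of 160 if the arms are equal, so 8 to 16 subjects would be 20% to 40% of the CSII arm's planned losses.

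**The case against.** The strongest reply is that the protocol already offers a route that keeps these people in follow-up. Section 9.12 treats the delivery method as a compliance matter and stops treatment only. Section 8.3.2 does the same for low compliance or more than 7 days off medication. SAP deviation 46 has failure to stay on the randomized method reviewed case by case, and SAP 5.4 plans to count subjects not treated by their assigned method and subjects who stopped treatment but completed. A reader might infer from 8.3.3 that every pump refuser must leave the study. The documents do not support that, because two routes exist. The retention route is not assured either: none of the three definitions of significant noncompliance in 9.12 names refusal of the assigned method, while 8.3.3 is mandatory and deviation 42 backs it.

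A reader might also infer that the losses fall almost only in the CSII arm. The text does not show this. Criterion [28] covers syringe use, glucose monitoring, diary and illness in both arms. MDI subjects must learn U-500R dosing with U-100 syringes, and former U-100 pump users can be randomized to injections.

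A third inference, that the rule empties the imputation reference set, fits only the protocol's same-arm reference. Under the later SAP the set is MDI-only, so CSII subjects never belong to it.

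Two further objections stand in part. Section 8.2.1 gives safety as the reason for [28], so some exits may be safety-driven. Some people unwilling to perform procedures would withdraw consent whatever the rule says. Neither explains why declining a delivery method should by itself end HbA1c sampling.

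**Conclusion.** The conflict is real. Section 8.3.3, backed by SAP deviation 42, requires study exit for a situation that 8.3.2, 9.12 and Section 11 would handle as a treatment stop with continued follow-up. The consequence is avoidable missing Week 26 HbA1c in the FDA-requested primary analysis.

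Arm imbalance is plausible, not demonstrated. The cost in power is small: about 1.4 points for 5% extra CSII losses and 3 points for 10%. The possible shift matters more, at 0.025 to 0.10 HbA1c points over the range shown, but it rests wholly on an assumed loss rate and gap. It also assumes that the true values are worse than the imputed ones; if they were better, the shift would reverse. With few [28] exits it would be negligible. This should be corrected, but it does not by itself undermine the trial.

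**What to change.** Reconcile Protocol 8.3.3 with 8.3.2, 9.12 and Section 11, and align SAP deviation 42, so that:
- meeting [28] after randomization does not by itself end follow-up;
- scheduled visits with HbA1c continue through Visit 17 unless the subject withdraws consent;
- a site that keeps such a subject in follow-up is not recorded as having an important deviation for that reason;
- missing Week 26 HbA1c is reported by arm and by reason, with [28] as its own category.

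What happens to the subject's treatment, and any exit needed for safety, stays with the clinical sections.

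The cost is a short amendment, a matching SAP edit and a site memo. The visits and samples are already in Attachment 1. The downside is some follow-up visits for subjects off their assigned method, and recovery will be incomplete because some will withdraw consent anyway.
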